Subjects will be switched to open-label tofacitinib 5 mg BID for the remainder of the study.

- Contact IWRS and dispense new supply of open-label investigational product to subject;
- Administer in-clinic dose of investigational product from open-label study drug supply.
- Instruct subject not to take the in-clinic dose of investigational product the day of the next study visit but to bring the drug supply with them to the visit.

6.2.7. Week 24

There is a ± 7 day window for this visit.

- All PROs should be completed prior to any other study procedures. These include the following: ASAS/ASDAS_{CRP} Component: “Patient Global Assessment of Disease (NRS)”, “Patient Assessment of Spinal Pain” which includes Total Back Pain (NRS) and Nocturnal Spinal Pain (NRS), BASDAI (NRS), BASFI (NRS), and FACIT-F.

After the PROs are obtained, the following procedures should be completed prior to dosing:

- Verify morning dose of investigational product was not administered by subject. If the dose was administered, continue with visit but re-instruct subject on the requirement for in-clinic dosing;

- Note: For subjects where the visit is conducted in the afternoon or evening, verify the afternoon or evening dose of investigational product was not administered by the subject. Vital signs: Blood pressure (seated), pulse rate and temperature (via tympanic, oral or temporal, preferred);
- Laboratory testing: Hematology, Chemistry Panel, Urinalysis, Urine Pregnancy Test (for women of childbearing potential only), hsCRP;
- Administer in-clinic dose of investigational product from previously dispensed study drug supplies.

The following procedures can be done before or after dosing depending upon the clinic's schedule but it is recommended that they be done at the same time (before or after dosing) consistently across all subsequent subject clinic visits:

- Targeted physical examination (examination of heart, lungs, abdomen, lower extremities, skin (presence of rash) and lymph nodes);
- Weight (without shoes preferred);
- BASMI (linear function) by qualified blinded assessor: Lateral spinal flexion, tragus-to-wall distance, lumbar flexion (modified Schober), maximal intermalleolar distance and cervical rotation;
- Spinal mobility obtained by qualified blinded assessor: chest expansion;
- Assessment of swollen joints (44-joint count) by qualified blinded assessor;
- Assessment of enthesitis using the MASES Index by qualified blinded assessor;
- Complete drug accountability.

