7.1.4. Complete Physical Examination

A standard complete physical examination will be performed at Screening, Baseline/Day 1, Week 16, and Week 48. The following parameters and body systems will be examined and any abnormalities described: general appearance, skin (presence of rash), HEENT (head, ears, eyes, nose, throat), lungs (auscultation), heart (auscultation for presence of murmurs, gallops, rubs), lower extremity exam (for peripheral edema), abdominal (palpation and auscultation), neurologic (mental status, station, gait, reflexes, motor and sensory function, coordination) and lymph nodes. Any clinically significant change(s) from Baseline/Day 1 should be recorded as an adverse event(s).

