7.1.6. Vital Signs

Body temperature, blood pressure and pulse rate will be measured at every study visit.

It is preferred that body temperature be collected using the tympanic, oral or temporal methods. The method chosen should be used consistently by the investigational site throughout the study.

Blood pressure (BP) will be measured using a standard calibrated blood pressure measuring device. The following method should be used to record the blood pressure:

- Subjects should be seated in a chair with feet flat on the floor, back supported and their arms bared (free of restrictions, such as rolled up sleeves, etc) and supported at heart level;
- Measurements should be taken on the same arm at each visit (preferably nondominant arm);
- Subjects should refrain from smoking or ingesting caffeine during the 30 minutes preceding the measurements;
- Measurements should begin after at least 5 minutes of rest;
- BP should be recorded to the nearest mmHg value.

When the timing of BP and pulse rate measurements coincides with a blood collection or other study procedures, BP and pulse rate should be obtained first.

7.1.7. 12-Lead Electrocardiogram (ECG)

Twelve-lead electrocardiograms (ECGs) will be obtained on all subjects at the Screening, Week 16, Week 48 visits. All ECGs should be performed after the subject has rested quietly for at least 10 minutes. ECG data will be submitted to a central reader for measurement. Any clinically significant changes from the Screening ECG will be recorded as adverse events and evaluated further, as clinically warranted.

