6.6.1. Adverse Events

AEs will be reported as treatment-emergent all causality and treatment-emergent treatment-related. A treatment-emergent AE is any event that starts on or after the first dosing day. The algorithm will not consider any events that start prior to the first dose date.

The relationship to study treatment is assessed by the investigator.

AEs will be displayed by two analysis periods: (1) Baseline to Week 16; and (2) Baseline to Week 48 (end of study including follow-up).

Tier-1 events, ie, AEs of special interest will be summarized descriptively.

Tier-2 events will be analyzed using asymptotic methods proposed by Miettinen and Nurminen (1985).¹¹ Risk ratios (tofacitinib 5 mg BID compared to placebo) and 2-sided 95% CI will be reported. P-values will not be reported for Tier-2 events. This analysis is applicable for the period of Baseline to Week 16 only.

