9.4. Definition and Use of Visit Windows in Reporting

For reporting purposes, the following visit windows will be used for efficacy, patient-reported outcomes and safety display that show by scheduled visits. If two or more observations fall into the same visit window, the observation closest to the target day will be used in the analyses. If there is a tie, the later observation will be used. However, for a subject who discontinues from the study early prior to the Week 48 visit and who does not have an observation within the Week 48 visit window, if two or more observations fall in the same visit window (ie, a visit window prior to Week 48), then the latest observation (rather than the observation closest to the target day) within this visit window will be used in the analysis for that visit window.

The visit windows will be applied to on-drug data and on-study data separately (see [Section 9.1](#)).

Table 5. Visit Windowing

Visit Label	Target Day ^a	Window Definition
Screening		< Day 1
Baseline	Day 1	Last non-missing assessment on or before Day 1 and prior to first dose of investigational product (ie, tofacitinib or placebo)
Week 2	Day 15	Day 2 to Day 21
Week 4	Day 29	Day 22 to Day 42
Week 8	Day 57	Day 43 to Day 70
Week 12	Day 85	Day 71 to Day 98
Week 16 ^c	Day 113	Day 99 to [Treatment Switch Day ^b or Day 140, whichever is smaller]
Week 24	Day 169	[Treatment Switch Day ^b +1 or Day 141, whichever is smaller] to Day 196
Week 32	Day 225	Day 197 to Day 252
Week 40	Day 281	Day 253 to Day 308
Week 48	Day 337	≥ Day 309

- a. Target day is equal to the target week×7 days + 1 day.
- b. Treatment switch day = day of the first dose of treatment switch at Week 16 (ie, treatment switch day = treatment switch date – date of the first dose +1), where treatment switch date is taken from the Oral Dosing CRF, as the start date in the first entry of the dosing log for the period of Week 16 to Week 24.
- c. All the data collected on treatment switch day will be counted in ≤ Week 16 except for the AE data. Any new treatment emergent AE occurred on the day of treatment switch will be counted in ≥ Week 24.

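### New AEs dated to the open-label switch day leave the placebo-controlled AE comparison, even when they began before the first open-label dose

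*SAP*

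**What the plan says.** Footnote c to Table 5 in SAP 9.4 has two parts. The first is "All the data collected on treatment switch day will be counted in ≤ Week 16 except for the AE data". The second sends the excepted events forward: "Any new treatment emergent AE occurred on the day of treatment switch will be counted in ≥ Week 24". Neither part asks whether the event began before or after the dose. Footnote b gives "Treatment switch day = day of the first dose of treatment switch at Week 16", with the date taken from the dosing log.

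Protocol 6.2.6 sets the order of the Week 16 visit. The questionnaires, ECG, laboratory tests, complete physical examination and AE monitoring come first. The move to open-label supply follows, and then: "Administer in-clinic dose of investigational product from open-label study drug supply".

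Findings from these assessments can become AEs. For the ECG, protocol 7.1.7 says: "Any clinically significant changes from the Screening ECG will be recorded as adverse events". Protocol 7.1.4 has the same requirement for the complete examination. Protocol 8.2.2 makes an abnormal test result an AE when one of its listed conditions is met.

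SAP 6.6.1 displays AEs for two periods, Baseline to Week 16 and Baseline to Week 48. Of the Tier-2 risk ratios it says: "This analysis is applicable for the period of Baseline to Week 16 only". It does not name the day on which the first period ends, so footnote c is the only text that settles this.

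**The concern.** The protocol places the Week 16 assessments ahead of the open-label dose. The SAP follows that order for every kind of data except AEs. One pre-dose finding can therefore be a Week 16 result as an ECG or laboratory value and a later event as an AE.

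Baseline to Week 16 is the only placebo-controlled AE comparison and the only one with a between-arm estimate and interval. In the placebo arm, a pre-dose event on the switch day arose before any tofacitinib was taken. In the tofacitinib arm the drug is the same before and after the switch, so there is no change of exposure to justify moving the event. At stake are the completeness of the controlled AE table and, for terms with few events, whether a Tier-2 risk ratio is produced at all.

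**Working it through.** The documents give no AE rates, so the size of the effect cannot be computed. The check sets the texts side by side and adds one illustration.

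**1. Where the switch day falls.** Table 5 gives "Target day is equal to the target week×7 days + 1 day". For Week 16 this is 16 × 7 + 1 = Day 113, as the table shows. With the ±7-day visit window the planned range is Day 106 to Day 120. That lies inside Day 99 to Day 140, the range in which SAP 9.4 lets the switch day close the Week 16 window. For a subject who follows the schedule, the visit day, the switch day and the last day of the Week 16 window coincide.

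**2. One finding followed through.** Take a new, clinically significant ECG change seen at Week 16, before the open-label dose, and recorded as an AE with that day as onset.

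| Record | Rule | Where it is counted |
|---|---|---|
| ECG value | Footnote c, first part | Week 16 |
| AE, Baseline to Week 16 display | Footnote c, second part | Not counted |
| AE, Tier-2 risk ratio | SAP 6.6.1, Baseline to Week 16 only | Not counted |
| AE, Baseline to Week 48 display | SAP 6.6.1 | Counted |

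No planned AE table covers the time after the switch on its own. Within these displays the clause can only take events out of the controlled comparison.

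**3. Scheduled on-treatment assessments up to Week 16** (Schedule of Activities).

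| Assessment | Weeks | Share at Week 16 |
|---|---|---|
| ECG | 16 | 1 of 1 |
| Complete physical examination | 16 | 1 of 1 |
| Lipid panel | 4, 16 | 1 of 2 |
| Hematology, chemistry | 4, 12, 16 | 1 of 3 |

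These shares count tests, not AEs. Targeted examinations at Weeks 2, 4, 8 and 12 cover lungs, heart, abdomen, lower extremities, skin and lymph nodes, and also generate AEs (protocol 7.1.4.1). AEs are collected at every visit.

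**4. Illustration with assumed counts, 120 per arm** (the planned size in protocol 9.1). The risk ratio is RR = (x1/120)/(x0/120), with x1 for tofacitinib and x0 for placebo. The interval is the Miettinen–Nurminen score interval: the values R at which (p1 − R·p0)²/V(R) = 1.96². Here V(R) = [q1(1 − q1)/n1 + R²·q0(1 − q0)/n0] × N/(N − 1), N = n1 + n0, and q1 = R·q0 are the rates fitted under R. SAP 3.5 makes a term Tier-2 when at least 4 subjects in either arm report it. I assume that this count is made within Baseline to Week 16.

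| Subjects, tofacitinib vs placebo | RR (95% CI) | Tier-2? |
|---|---|---|
| 4 vs 2 | 2.00 (0.44 to 9.25) | Yes |
| 3 vs 2, one tofacitinib event moved | none produced | No |
| 8 vs 4 | 2.00 (0.66 to 6.13) | Yes |
| 7 vs 4, one tofacitinib event moved | 1.75 (0.56 to 5.50) | Yes |
| 6 vs 4, two tofacitinib events moved | 1.50 (0.46 to 4.86) | Yes |
| 8 vs 3, one placebo event moved | 2.67 (0.79 to 9.13) | Yes |

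The ratio can move either way, and every change is small beside the width of the intervals. The clearest effect is on a term at the four-subject threshold.

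**The case against.** The strongest defence is that the rule is prespecified, gives both arms the same boundary, and supplies a default when the onset time is unknown. Sending doubtful events to the post-switch side could also be seen as cautious, because it charges placebo-arm events to active drug. The first part stands: a default is needed, and this one is symmetric by design. The second does not, because SAP 6.6.1 has no post-switch display in which such a charge would appear.

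Several limits also stand:

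- Only new AEs with onset on that one day move. Events elicited at the Week 16 query with earlier onset stay in Baseline to Week 16.
- Protocol 6.2.6 allows blood to be drawn up to 48 hours before or after the visit. An AE dated to an earlier sample stays in the controlled period; one dated to a later sample is truly post-switch.
- Protocol 8.2.2 makes a laboratory abnormality an AE only under its listed conditions.
- The documents do not say what onset date a test-detected AE receives. ECGs are read centrally and blood is tested centrally, so the recorded date need not be the visit day.
- Test values remain in the Week 16 summaries, the AEs remain in Baseline to Week 48, and Tier-2 results carry no p-values.

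A reader might infer that every AE revealed by the Week 16 ECG, examination or laboratory tests drops out. The documents do not support that, because it requires each such AE to take the visit day as onset. A reader might also infer a bias in favour of tofacitinib. The rule moves events in both arms, so the direction is not known.

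**Conclusion.** Footnote c is inconsistent with the protocol's visit order. It takes new switch-day AEs, including those that began before the open-label dose, out of the only placebo-controlled AE comparison. It does so without assigning them to any separate post-switch display.

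The size and direction are unknown and the effect is probably small. The conclusion assumes that footnote c governs the AE periods in SAP 6.6.1, since nothing else sets the boundary, and that the switch takes place at the Week 16 visit as planned. One asymmetry is possible. A subject who stopped investigational product before Week 16 would, by inference from footnote b, have no switch day and would keep visit-day AEs in the controlled period. Unequal discontinuation would then make the effect unequal between arms. The efficacy analyses are not affected.

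**What to change.** State in SAP 6.6.1 the day on which Baseline to Week 16 ends for AEs. Then repeat the Baseline to Week 16 AE tables and the Tier-2 risk ratios with switch-day AEs included, selecting the Tier-2 terms afresh, so that a term reaching four subjects only with those events is shown.

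Alternatively, amend footnote c so that switch-day AEs known to have begun before the open-label dose count in Baseline to Week 16. That version still needs a default for events of unknown timing; showing both sets of tables avoids the choice.

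No new AE-page field is needed. SAP version 4 followed a blinded data review, so a before-or-after-dose field could probably not have been collected prospectively for every subject. The cost is a sentence in the SAP and one additional set of tables from data already held. The drawback is that some switch-day events of unknown timing in the repeated tables may have begun after the dose.

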5.2. General Methods

As subjects randomized to treatment group of placebo → tofacitinib 5 mg BID (ie, → means switching to) will advance from placebo to open-label treatment of tofacitinib 5 mg BID at Week 16, the treatment label used for reporting visits up to Week 16 will be “Placebo” and treatment label for reporting visits after Week 16 through Week 48 will be “Placebo → Tofacitinib 5 mg BID”. For analyses through Week 16, the following treatment comparison will be made at each time point, where applicable:

- Tofacitinib 5 mg BID vs. Placebo.

For analyses after Week 16 through Week 48, the following treatment comparison will be made at each time point,

- Tofacitinib 5 mg BID vs. Placebo → Tofacitinib 5 mg BID.

The primary efficacy comparison for the primary endpoint of ASAS20 will be between tofacitinib 5 mg BID and placebo at Week 16.

Descriptive Summaries

In general, the data for all continuous endpoints will be summarized by treatment group (ie, 2 groups) and by time point in tables containing descriptive statistics (N [which is the number of subjects evaluable for the endpoint at the time point], mean, standard deviation, standard error of the mean, minimum, 1st, 2nd (ie, median) and 3rd quartiles and maximum) for actual and change from Baseline (or percent change from Baseline) values for those endpoints measured at Baseline. In case when N=1 (ie, only one subject is

available/evaluable for summary), standard deviation and standard error will be reported as “NA” (not applicable) while the remaining statistical parameters will have the same value as the mean. The data for all response-type endpoints will be summarized by treatment group and by time point in tables showing descriptive statistics: N, n (ie, number of responders), response rate (%), standard error of the response rate, and 95% confidence interval (CI) based on normal approximation. If \hat{p} is the estimated response rate, then the 95% CI is calculated as:

$$\hat{p} \pm z_{0.975} \sqrt{\frac{\hat{p}(1 - \hat{p})}{N}}$$

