6.1.1. Primary Analysis

The ASAS20 response rate at Week 16 is the primary efficacy endpoint in this trial. The analysis of primary endpoint will be based on the FAS, which includes all randomized subjects who take at least 1 dose of investigational product (ie, tofacitinib or placebo). For the primary analysis, the normal approximation for the difference in binomial proportions adjusting for the stratification factor (ie, prior treatment history: "bDMARD-naïve" vs "TNFi-IR or bDMARD Use [Non-IR]") at randomization (prior treatment history will be derived from the clinical database and used in the analysis; see [Section 3.4.1](#) and [Section 9.11](#)) via the CMH approach will be used to test the superiority of tofacitinib 5 mg BID to placebo and to generate 95% CI for the difference (see [Section 5.2.1.1](#)). Missing values for any reason will be handled by setting the ASAS20 value to nonresponsive, MR=NR (see [Section 5.3](#)). This is the primary analysis for the ASAS20 response rate at Week 16. This analysis uses the on-drug data only (see [Appendix Section 9.1](#)). This corresponds to Estimand 1 or the Primary Estimand (see [Section 2.1.1](#)). Analysis of ASAS20 at other time points will also be analyzed using the same method and the on-drug data on the FAS.

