Note that the upper limit of the Week 16 visit window and the lower limit of the Week 24 visit window are defined uniquely for each of the subjects in the study regardless of which treatment group the subjects are randomized to, since per the study protocol, subjects randomized to the placebo → tofacitinib 5 mg BID treatment group will advance to the predetermined treatment (tofacitinib 5 mg BID) in a blinded fashion for the remainder of the study. Further details for the Week 16/Week 24 visit windows are in order.

1. If treatment switch day falls between Day 99 and Day 140, then the upper limit of the Week 16 visit window is the smaller of treatment switch day or Day 140 and the lower limit of the Week 24 visit window is the smaller of treatment switch day+1 or Day 141;
2. If treatment switch day < 99, >140, or missing, then the upper limit of the Week 16 visit window will be set to Day 140 and the lower limit of the Week 24 visit will be set to Day 141.

Effects of Bullets 1 and 2 above are further illustrated as follows.

Visit label	If treatment switch day is							
	Missing		<99		99-140		>140	
	Week 16	Week 24	Week 16	Week 24	Week 16	Week 24	Week 16	Week 24
Day window	99 to 140	141-196	99 to 140	141-196	from [99 to 99] up to [99 to 140]	from [100 to 196] up to [141 to 196]	99 to 140	141-196

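### For a Week 16 visit held after Day 140, the window rules in SAP 9.4 conflict, and pre-switch placebo data can be reported as Week 24 data after the switch to tofacitinib

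*SAP*

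**What the plan says.** Three places in SAP 9.4 agree with each other. Table 5 ends the Week 16 window at the earlier of the treatment switch day and Day 140, and starts Week 24 at the earlier of switch day + 1 and Day 141. The second numbered rule below the table opens "If treatment switch day < 99, >140, or missing, then the upper limit of the Week 16 visit window will be set to"; the limit it then gives is Day 140, and Week 24 starts one day later. The illustration table has a column for a switch after Day 140, with Week 16 as Days 99 to 140 and Week 24 as Days 141 to 196.

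Footnote c, attached to the Week 16 row of Table 5, says "All the data collected on treatment switch day will be counted in ≤ Week 16 except for the AE data". It carries no upper day limit.

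Four other statements determine what follows:

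- Protocol 6.2.6 lists the Week 16 assessments first and then: "Administer in-clinic dose of investigational product from open-label study drug supply". SAP 9.4, footnote b, defines the switch day as the day of that first dose. The switch-day efficacy record is therefore normally the blinded Week 16 assessment.
- SAP 6.1.1: "Missing values for any reason will be handled by setting the ASAS20 value to nonresponsive, MR=NR". SAP 6.2 applies the same method to ASAS40.
- SAP 9.4, where a window holds several records: "the observation closest to the target day will be used in the analyses". The exception is a subject who leaves the study before Week 48 and has no record in the Week 48 window; the latest record in the window is then used.
- SAP 5.2, for subjects randomized to placebo: "treatment label for reporting visits after Week 16 through Week 48 will be" Placebo → Tofacitinib 5 mg BID.

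**The concern.** For a switch on Days 99 to 140, the SAP starts Week 24 the day after the switch, so no pre-switch observation can enter a post-switch visit. For a switch after Day 140 that protection is lost: Week 24 opens on Day 141 whether or not the switch has happened. Footnote c would keep the switch-day data out of Week 24, but it contradicts the three statements above, and the SAP does not say which prevails.

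Two results depend on the choice. One is whether an observed Week 16 response is used or set to non-response in the primary and key secondary analyses. The other is whether an assessment made before any tofacitinib was taken can be shown as a Week 24 result after the switch to tofacitinib.

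**Working it through.** **Target days and window limits.** SAP 9.4: "Target day is equal to the target week×7 days + 1 day".
- Week 16: 16 × 7 + 1 = 113. Week 24: 24 × 7 + 1 = 169. Week 32: 32 × 7 + 1 = 225.
- Midpoints: (113 + 169)/2 = 141 and (169 + 225)/2 = 197. These reproduce the Table 5 starting days for Week 24 (without an earlier switch) and Week 32.
- Protocol visit window for Week 16: 113 ± 7 = Days 106 to 120. Day 141 is 141 − 120 = 21 days past it.

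**Where the switch-day assessment falls.**

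| Switch day | Week 16 window | Week 24 window | Visit by Table 5 and numbered rules | Visit by footnote c |
|---|---|---|---|---|
| 113 | 99-113 | 114-196 | Week 16 | Week 16 or earlier |
| 140 | 99-140 | 141-196 | Week 16 | Week 16 or earlier |
| 141 | 99-140 | 141-196 | Week 24 | Week 16 or earlier |
| 145 | 99-140 | 141-196 | Week 24 | Week 16 or earlier |

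The rules agree up to Day 140 and conflict from Day 141.

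**Effect at Week 16 under the Day 140 cap.** A Week 12 visit within its protocol window (85 ± 7 = Days 78 to 92) stays in the Week 12 window (Days 71 to 98), so Days 99-140 are normally empty. ASAS20 and ASAS40 are then non-response. MMRM, ANCOVA and GMMRM treat the value as missing, and the tipping point analysis imputes a result that was in fact observed.

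**Effect at Week 24 (Week 48 analysis only).** For a switch on Day 145:
- Distance to Day 169 is 169 − 145 = 24 days. A Week 24 visit on Days 162-176 is at most 7 days away and displaces the pre-switch record. This holds for every switch day from 141 to 162.
- If the Week 24 visit is missed, the Day 145 record is the only one in the window and is used.
- If the site re-times visits from the switch (an assumption), the next visit is 145 + 56 = Day 201, in the Week 32 window. The Day 145 record is again the Week 24 value.

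The false label arises only in the placebo arm, because the other arm was already assigned to tofacitinib.

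**Size for the primary endpoint.** Inputs from Protocol 9.1: 120 per arm, 60% versus 40%, two-sided 5%. With the unpooled variance of SAP 5.2.1.1, power is Φ(0.20/√(0.24/120 + 0.24/120) − 1.96) = 88.5%, against the stated figure of about 89%. One responder reclassified lowers an arm's rate by 1/120 = 0.83 points. With k affected subjects in an arm, the expected rate is p × (1 − k/120). The documents do not give k; the values below are assumptions.

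| Affected (tofacitinib / placebo) | Expected difference (points) | Power |
|---|---|---|
| 0 / 0 | 20.0 | 88.5% |
| 1 / 1 | 19.8 | 88.0% |
| 3 / 3 | 19.5 | 86.9% |
| 3 / 0 | 18.5 | 83.1% |
| 0 / 3 | 21.0 | 91.4% |

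**The case against.** The best defence is that the SAP already gives a worked answer. Table 5, the second numbered rule and a dedicated column of the illustration table all say the same thing, and footnote c can be read as a tie-break for the usual case in which the switch day is the boundary. The Day 140 cap is also ordinary midpoint windowing: Day 145 is 32 days from the Week 16 target and 24 from the Week 24 target. This largely stands. It makes the conflict over Week 16 a matter of footnote wording and leaves the cap defensible. It does not justify placing a pre-switch record in a post-switch visit.

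A reader might infer that any late switch turns an observed Week 16 result into non-response. The documents do not support that. The assessment itself must be after Day 140. A subject assessed on Day 113 whose first open-label dose is logged after Day 140 keeps the Week 16 value, and so does anyone with another usable record in Days 99-140.

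Nor do the documents show that such subjects were still taking blinded product up to the switch. Protocol 5.4.2 provides supply to the next scheduled visit, and Protocol 6.4.2 makes an interruption of more than 5 consecutive days in the double-blind period a reason for discontinuation. A subject who discontinued product before Week 16 is a non-responder under Estimand 1 in any case.

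The Week 24 consequence is confined to the Week 48 analysis, which SAP section 5 calls secondary, and a timely Week 24 visit prevents it.

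**Conclusion.** SAP 9.4 contradicts itself for a subject whose Week 16 assessment and first open-label dose both occur after Day 140. Its numbered rule can also report pre-switch placebo data as Week 24 under the post-switch label. The second defect is the firmer one, because the SAP guards against it for switches on Days 99-140 and drops the guard afterwards.

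The effect on the primary result is likely negligible. The case requires a visit at least 21 days outside its window, and one affected subject per arm moves the expected difference from 20.0 to 19.8 points. The larger shifts in the table need three affected subjects confined to one arm, which nothing in the documents suggests. It would be wrong to read this as a bias in the primary analysis, or as showing that the Day 140 cap must go.

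The conclusion assumes that the late assessment is made on the switch day, as Protocol 6.2.6 has it. The Week 16 effect also assumes nothing else in Days 99-140. The Week 24 effect assumes no record closer to Day 169 or, for a subject who leaves the study early, no later record in the Week 24 window.

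**What to change.** For a switch day after Day 140, change Table 5, the second numbered rule and the illustration table as follows:

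1. Admit to Week 24 only observations after the switch day. The window runs from switch day + 1 to Day 196, and there is no Week 24 value if the switch is on Day 196 or later. Apply the same bar on pre-switch records to every later window.
2. State which rule governs Week 16. If the Day 140 cap is kept, limit footnote c to switch days on or before Day 140, and list the subjects who have a blinded assessment after Day 140.

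If the sponsor would rather let footnote c govern Week 16, the extended window needs its own end day and selection rule. Without them it could run into Week 32 (from Day 197), or, for an early leaver, the latest-record rule could replace an on-time Week 16 value with a much later one.

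The cost is a few words in SAP 9.4 and a small change to the windowing program, made before unblinding for the Week 16 analysis. A few subjects would have no Week 24 value, which counts as non-response for binary endpoints and as missing in MMRM.

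### For a switch to open-label drug before Day 99, the SAP's Week 16 window (Days 99-140) holds only post-switch days and conflicts with Table 5, so the blinded Week 16 assessment cannot be used as Week 16

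*SAP*

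**What the plan says.** SAP 9.4, Table 5, gives Week 12 the window "Day 71 to Day 98" (target Day 85). Week 16 (target Day 113) runs from Day 99 to the switch day "or Day 140, whichever is smaller". Week 24 opens on the earlier of the day after the switch and Day 141. Footnote b defines the term: "Treatment switch day = day of the first dose of treatment switch at Week 16".

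The bullets under the table treat two cases. The first repeats Table 5 for switch days 99 to 140. The second covers a switch day that is below 99, above 140 or missing: "then the upper limit of the Week 16 visit window will be set to Day 140", with Week 24 opening on Day 141. The illustration that follows has a separate column for a switch day below 99 and repeats Days 99-140 and 141-196.

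Three other rules bear on the point:

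- When two observations share a window, "the observation closest to the target day will be used in the analyses", with ties going to the later one. A subject who leaves the study before Week 48 and has no observation in the Week 48 window is treated differently: the latest observation in the window is used.
- Footnote c: "All the data collected on treatment switch day will be counted in ≤ Week 16 except for the AE data".
- SAP 9.1 cuts on-drug data only at permanent discontinuation of investigational product. SAP 6.1.1 sets a missing Week 16 ASAS20 to non-response.

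Protocol 5.4.1 and 6.2.6 place the first open-label dose in the clinic at the Week 16 visit, after that visit's assessments.

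**The concern.** Ending Week 16 at the switch keeps open-label data out of the randomised comparison. For an early switch, the second bullet does the reverse: the window opens only after the switch and stays open to Day 140. The assessment that closed the blinded period lies outside it.

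The primary endpoint, the key secondary endpoint and every Type I error controlled secondary endpoint are read at Week 16. At stake is which value, if any, represents such a subject. The second bullet and Table 5 also give different windows for the same subject, so two programmers following the SAP could build different datasets.

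**Working it through.** **Inputs.** Windows, target days and selection rule: SAP 9.4. Visit windows of ±7 days: Protocol Schedule of Activities. 120 subjects per arm, planned as 96 and 24 by stratum: Protocol 5.1 and 9.1. Planning rates of 40% on placebo and a 20-point difference: Protocol 9.1.

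**1. Reproduce the SAP's illustration and compare it with Table 5.** For switch day s, Table 5 gives Week 16 = Day 99 to min(s, 140) and Week 24 = min(s+1, 141) to Day 196.

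| Switch day | Bullets: Week 16 / Week 24 | Table 5: Week 16 / Week 24 | Label of switch-day visit |
|---|---|---|---|
| 85 | 99-140 / 141-196 | empty / 86-196 | Week 12 |
| 92 | 99-140 / 141-196 | empty / 93-196 | Week 12 |
| 98 | 99-140 / 141-196 | empty / 99-196 | Week 12 |
| 99 | 99-99 / 100-196 | 99-99 / 100-196 | Week 16 |
| 113 | 99-113 / 114-196 | 99-113 / 114-196 | Week 16 |

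The bullets match the SAP's illustration. For every switch day from 1 to 98, all 140 − 99 + 1 = 42 days of the Week 16 window come after the switch. Table 5 read literally does not solve the problem: with a switch on Day 92, its Week 24 window (93-196) overlaps Week 12 on Days 93-98.

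**2. What happens to the blinded Week 16 assessment.** In Days 71-98 it competes with the true Week 12 visit for closeness to Day 85.

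- Week 12 visit on Day 85: nothing on Days 86-98 can be selected.
- Week 12 visit on Day 82: the early visit is selected only up to Day 88.
- Week 12 visit on Day 78: it is selected up to Day 92 (|92 − 85| = |78 − 85| = 7, and the later one wins).

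Otherwise it is discarded, unless the latest-observation rule for early leavers applies. On Day 70 or earlier it falls in an earlier window.

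**3. What can fill Days 99-140.** The next scheduled visit is Week 24: 24×7 + 1 = 169, ±7 = Days 162-176, outside the window. Week 16 is therefore usually empty. It can be filled only by off-schedule data, and SAP 9.1 does not remove such data. One narrow route for a single laboratory endpoint is that Protocol 6.2.6 allows blood up to 48 hours after the visit. With a switch on Day 97 or 98, an hsCRP sample on Day 99 or 100 would become the Week 16 value.

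**4. Effect by endpoint.** ASAS20 and ASAS40 become non-response. ASQoL and SF-36v2 are collected only at Baseline, Week 16 and Week 48, so the subject drops out of the Week 16 ANCOVA (SAP 5.2.3). MMRM endpoints lose the Week 16 observation.

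**5. How rare.** Week 16 target: 16×7 + 1 = 113, ±7 = Days 106-120. Day 98 is 106 − 98 = 8 days before that window opens.

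**6. Size per subject.** The crude arm rate moves by at most 1/120 = 0.83 points. The CMH-weighted difference gives the same. Stratum weights are proportional to 96×96/192 = 48 and 24×24/48 = 12, ie 0.8 and 0.2, and 0.8/96 = 0.2/24 = 0.83 points. Two, three or six subjects in one arm give at most 1.7, 2.5 or 5.0 points; these counts are illustrative.

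**7. Direction, on average, at the planning rates (40% and 60%).**

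- Placebo subject set to non-response: 0.4/120 = 0.33 points, widening the difference.
- Tofacitinib subject set to non-response: 0.6/120 = 0.50 points, narrowing it.
- Placebo subject given an open-label value, assuming that value responds at 60%: 0.2/120 = 0.17 points, narrowing it.

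**The case against.** The other side has several fair arguments.

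- **Footnote c.** A reader might infer that the second bullet contradicts it. It does not: the footnote places switch-day data at or before Week 16, and Week 12 satisfies that. The conflict is with Table 5.
- **Contamination.** A reader might infer that open-label values routinely enter the placebo arm. The documents do not support this. No scheduled visit falls in Days 99-140 after an early switch, unplanned visits are meant for subject welfare, and ASAS20 is missing if any of its four domains is missing (SAP 9.2.1). The usual result is a missing value.
- **Non-response is the stated estimand.** Response requires completing the visit of interest (SAP 5.3), and the tipping-point analyses vary the missing values. This holds for a subject who was not assessed. Here the subject did complete the visit, and the value is lost through labelling. The tipping-point analyses would impute an observed outcome, and would not detect an open-label value taken as Week 16.
- **Too early to count as Week 16.** Day 98 is 15 days before target. Declining to use it is defensible, but the window would then have to be empty, not filled with open-label days. The SAP already accepts Day 99, 14 days early, and Day 140, 27 days late.
- **Unreliable dates.** The switch day comes from one dosing-log entry. If a date below 99 is an error, the default window is reasonable. That stands, and the fix should apply only to confirmed dates.

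**Conclusion.** The point holds as a small defect in a prespecified rule. For a genuine switch before Day 99, the second bullet defines a Week 16 window that cannot contain blinded data, and Table 5 defines an empty one. The result is usually an assessed subject counted as a non-responder. Less often it is an open-label value reported under the randomised arm, including placebo.

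The effect is at most 0.83 points per subject on ASAS20 or ASAS40, in either direction. This rests on 120 analysed per arm at the planned stratum sizes, and on the first open-label dose being given at the Week 16 visit. The number affected is not in the documents, and the visit windows suggest it is very small. A reader might infer that the primary conclusion is in doubt; nothing in the documents supports that. It is worth correcting because the rule feeds the primary endpoint and the correction is cheap.

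**What to change.** Remove the below-99 case from the second bullet and from the illustration, and limit Table 5's formula to switch days of 99 or later. Add one bullet for a switch day below 99 that is confirmed against source:

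- Week 16 is the assessment from the nominal Week 16 visit, on or before the switch day. If there is none, Week 16 is missing, and the Week 12 visit is not carried forward.
- That visit and all post-switch days are excluded from the Week 12 window, and from any earlier window they would fall in.
- No post-switch value is used for Week 16. Post-switch values go to Week 24 or later, with Week 24 opening the day after the switch. The exclusion above prevents overlap with Week 12.

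The cost is one SAP bullet, an edit to Table 5 and the illustration, and a programming condition that uses the nominal visit label. The number of subjects concerned can be read from dosing dates without unblinding. The downside is that a Week 16 value may lie more than 14 days before target; a listing can flag these.
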